## **5. Research Methodology**

### **5.1. Methods and Settings**

This is a prospective and cross sectional study. The study will be conducted in Rwanda at the University Teaching Hospital of Kigali from January to December 2021.

Rwanda is a country of 11.9 million in East Africa. There are approximately 80,000 surgical procedures performed annually in Rwanda, 510 major operations per 100,000 populations (30). Rwanda has 4 main referral hospitals performing surgical operations including laparoscopic procedures. The referral hospitals include: University Teaching Hospital (CHUK), University Teaching Hospital of Butare (CHUB), Rwanda Military Hospital (RMH) and King Faisal Hospital, Kigali (KFH, K)

The University Teaching Hospital of Kigali (CHUK) is the major public, tertiary referral and teaching hospital in Rwanda and it is located in the capital in Kigali. It has 565 beds and 11 operating theaters shared among all surgical services. It provides approximately up to 1600 major operative cases in general surgical services every year including 140 cases of laparoscopic surgeries with 75 cases of laparoscopic cholecystectomies. The CHUK started performing laparoscopic surgery routinely long time before others and currently it performs more than 60% of laparoscopic surgeries performed in the Country in different specialties including general surgery, Urology and Gynecology. Considering the above reason, we selected this hospital to represent others and be the site of our research interest.

This study will be conducted in general surgical unit at the University Teaching Hospital of Kigali (CHUK), it has a capacity of 2 operating rooms with 2 lap towers with complete sets of laparoscopic material and around 40 in patient beds.

The population proportion of laparoscopic cholecystectomy is 5% within a total general surgical population size of 1600 patients per year. A range of 50 to 70 patients will allow to have a confidence level of 95% that the real value is within  $\pm 5\%$  of the measured value and have relevant conclusions.

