## **2. Problem statement**

All surgeries, including laparoscopic surgery, represent a major stressor to the patient with possible sequelae for post-operative well being, including decline in functional capacity, cognitive ability, and even cancer spread. Comorbidities such as diabetes, ischemic heart and vascular disease, stroke, and others have a larger impact on postoperative morbidity and mortality than age (21) (10).

ERAS pathways have been successfully implemented in many surgical specialties, including gastrointestinal, hepato-biliary, pancreatic, urologic, gynecologic, and urologic surgery (22) (23) (24).

The strongest evidence so far has been described in patients undergoing open colorectal procedures (6) (25) (26). Combining minimally invasive laparoscopic surgery and ERAS has been shown to have important clinical and economic benefits and significant reductions in length of hospital stay, but its spread remains slow worldwide.

Implementation of ERAS pathways improves clinical outcomes and induces substantial economic gains (15) (16) (2), and is becoming the optimal strategy for many surgeries when technically feasible (27) (28) (10).

Laparoscopic cholecystectomy can be performed as a day-case procedure with a low rate of complications and admissions/readmissions. Patient acceptance in terms of quality of life variables is similar to that for cholecystectomy with an overnight stay. The day care strategy is associated with a reduction in cost (29).

Laparoscopic cholecystectomy in ERAS program should optimize the surgical outcome and improve a quick recovery and decrease the length of hospital stay. At the University Teaching of Kigali, the current practice is to admit patients for laparoscopic cholecystectomy 24 hours prior to surgery and to discharge most patients within two to three days of surgery with a rate of complications around 5%.

Patients overcrowd CHUK and the hospital bed management is a serious challenge. Patients coming far from their homes and with limited financial resources are suffering to get admitted in hospital for elective and none urgent surgeries like cholecystectomy, We believe that ERP can benefit the hospital with a rapid bed turnover rate, and reduces cost for surgery and hospitalization while providing to the patients with quality care and the same time increasing the comfort of the patient in the post-operative period and minimizing the postoperative complications.

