### **4.2. Specific Objectives**

1. To assess the level of knowledge and practice of Health care professional about Enhanced recovery after surgery program.
2. To determine the frequency of postoperative adverse events and complications after laparoscopic cholecystectomy (tress, fatigue, nausea and vomiting)
3. To determine the average length of hospital stay and bed turn over after laparoscopic cholecystectomy
4. To determine the rate and reason of overnight and re-admissions
5. To assess the patients' acceptance of ERAS program and the overall satisfaction
6. To determine the patient cost benefit when ERAS is implemented correctly.

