#### **5.3. Data collection and analysis**

A baseline survey will be conducted to assess the awareness and knowledge of health care professional in charge of perioperative care. From November 2021, we will put in place an ERAS protocol for laparoscopic cholecystectomies. Patients living in Kigali and near Kigali having an easy communication means will be sensitized to adhere to the program.

A multidisciplinary team (Surgeons, Anesthesiologists, nurses, anesthetists and psychologists) will be mobilized to participate in the team. A google sheet questionnaire will be designed to collect information about the awareness and knowledge of perioperative health care professional about ERAS programme and then

a modified ERAS protocol will be put in place and data collection will be done using a coded checklist form and consecutive selection of patients will be done during the study period until we reach at least 50 patients. The operative procedures and instrumentation will be standardized for laparoscopic cholecystectomy, and surgeons who will perform the procedures will be having expertise in laparoscopic cholecystectomy. Reasons for conversion from laparoscopic to open cholecystectomy will be recorded and documented. Emergency patients and patients defined as ASA IV and pediatric patients aged below 16 years will be excluded.

Data will be collected for age, gender, indications for surgery, American Society of Anesthesiology (ASA) class, operative time, adverse events (pain, nausea and vomiting), length of hospitalization, and intra- and post-operative complications. The expenses of surgery and in-hospital care will be calculated and analyzed. On discharge, on day 3 of discharge, day 10, day 15 and day 30 of discharge patient will report outcomes and will be recorded by Surgical Recovery Scale. After discharge, the patients will be called or texted on phone to know about their status and collect information. Data will be recorded using EXCEL. Statistical analysis will be done using SPSS software and the one-way analysis of variance (ANOVA) test, the Chi-square test, and the t Student's test will be used when appropriate for comparisons.

A Univariate analysis will be done to determine variables associated with the length of hospital stay. Pearson's chi square will be calculated to compare variables and..

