## **6. Expected Results**

Table 1: Level of awareness and knowledge of ERAS among perioperative care health professionals

Table 2: Baseline characteristics of patients

Table 2: Acceptance rate of patients in ERP

Table 3: Rate of adverse events (Stress, fatigue, pain, nausea and Vomiting)

Table 4: Complications of laparoscopic cholecystectomy

Table 5: The average length of hospital stay

Tableau 6: Cost of laparoscopic cholecystectomy

Table 7: Rate of overnight and readmission

Table 8: Overall satisfaction of patients after laparoscopic cholecystectomy in ERP

Table 9: Comparative analysis of length and independents variables

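### The ±5% precision claim for 50 to 70 patients rests on the operation's caseload share, which is not a study outcome; the usual formula gives 70 to 73 patients, and outcome rates of 10% to 50% would be less precise at either size

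*Protocol*

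**What the plan says.** The sample-size rationale is two sentences at the end of Protocol section 5.1. The first reads "The population proportion of laparoscopic cholecystectomy is 5% within a total general surgical population size of 1600 patients per year". The second begins "A range of 50 to 70 patients will allow to have a confidence level of 95% that the real value is within" and gives the margin as ±5%. No formula is shown and no outcome is named. Earlier in the same section the annual volume is given as "75 cases of laparoscopic cholecystectomies".

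Section 5.3 makes the lower end operative: consecutive patients are taken "until we reach at least 50 patients".

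The quantities to be estimated are in sections 4.2 and 6. They include adverse events and complications, "To determine the rate and reason of overnight and re-admissions", "To determine the average length of hospital stay and bed turn over after laparoscopic cholecystectomy", "Acceptance rate of patients in ERP", satisfaction and cost. None of them is the operation's share of the surgical caseload.

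**The concern.** The 5% describes how common the operation is among all general surgical cases. In the study sample that share is 100% by design, so a margin around it carries no information about any result the study will report.

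This is the protocol's only statement of precision. A reader would naturally apply ±5% to the complication, overnight-stay, readmission and acceptance rates. If the true margins are wider, the feasibility and safety results will look firmer than 50 to 70 patients can make them. The lower end matters most, because recruitment may stop there.

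**Working it through.** **Inputs.** From section 5.1: 95% confidence, two-sided because the margin is ±, so z = 1.96; d = 5 percentage points; p = 5%; N = 1600; 75 cholecystectomies a year. From section 5.3: minimum n = 50. Outcome rates of 10%, 20% and 50% are assumptions. The day-case success of 69–92% cited in section 1 (8–31% failure) shows that rates of this order are plausible.

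**Step 1: the plan's own figure.** Formula: n₀ = z²p(1−p)/d², corrected n = n₀/(1 + (n₀−1)/N).
- p = 5%: n₀ = 1.96² × 0.05 × 0.95 / 0.05² = 72.99, so 73. Corrected for N = 1600: 72.99/(1 + 71.99/1600) = 69.85, so 70.
- Unrounded share, 75/1600 = 4.69%: 68.65, so 69; corrected 65.87, so 66.

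The upper end of the range is reproduced. The lower end is not.

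**Step 2: precision at the minimum.** Half-width = 1.96 × √(0.05 × 0.95/50) = 6.04 points, or 5.95 with the N = 1600 correction. At n = 70 it is 5.11, or 4.99 corrected.

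**Step 3: the other reading of the sentence.** Take the claim as the chance that the estimate lands within 5 points of the truth, by exact binomial.

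| True rate | n = 50 | n = 70 |
|---|---|---|
| 5% | 96.2% | 97.7% |
| 75/1600 | 91.6% | 95.5% |
| 10% | 76.6% | 84.2% |
| 20% | 62.4% | 70.5% |
| 50% | 52.0% | 59.7% |

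**Step 4: half-widths for outcome rates.** In points, without a finite-population correction. The first figure is the normal approximation 1.96 × √(p(1−p)/n). The second is the expected Clopper-Pearson half-width, averaged over the binomial distribution of the count.

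| True rate | n = 50 | n = 70 |
|---|---|---|
| 5% | 6.0–6.9 | 5.1–5.7 |
| 10% | 8.3–9.0 | 7.0–7.6 |
| 20% | 11.1–11.7 | 9.4–9.8 |
| 50% | 13.9–14.3 | 11.7–12.1 |

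Over 10% to 50% this is 7.0/5 = 1.4 to 14.3/5 = 2.9 times the stated margin. The same widths hold at the mirror-image rates of 90% and 80%.

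**Step 5: correcting to one year's operated patients.** Multiply the normal half-width by √((N−n)/(N−1)), with N = 75 (stated volume) or 80 (5% of 1600).

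| True rate | n = 50 (N = 75 / 80) | n = 70 (N = 75 / 80) |
|---|---|---|
| 10% | 4.8 / 5.1 | 1.8 / 2.5 |
| 20% | 6.4 / 6.8 | 2.4 / 3.3 |
| 50% | 8.1 / 8.5 | 3.0 / 4.2 |

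**Step 6: mean length of stay.** The half-width is t(0.975, n−1)/√n standard deviations: 0.28 SD at n = 50 and 0.24 SD at n = 70. The protocol gives no SD, so this cannot be put into hours.

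**The case against.** Four points can be made for the plan.

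- **The current complication rate is also about 5%.** Section 2 describes present practice "with a rate of complications around 5" per cent. For that outcome 70 patients give roughly the stated precision. This stands, but section 5.1 does not cite that rate, and 50 patients still give about ±6 points.
- **Fifty is not plainly wrong at 5%.** A reader might infer that 50 fails on any reading. It does not: at a true rate of exactly 5%, the exact chance of landing within 5 points is 96%. The support is fragile, since it falls to 92% at the protocol's own 75/1600 and to 77% at 10%. The statement that 50 is too few therefore belongs to the normal-approximation formula.
- **A smaller population would narrow the margins.** A reader might also infer that ±5 points is unattainable by any method at rates of 10% or more. Step 5 shows otherwise: corrected to 75–80 patients, n = 70 stays under ±5 throughout, and n = 50 reaches about ±5 at 10%, though ±8 to 9 at 50%. Using 80 as the population even yields sizes of 51 (at 10%) and 67 (at 50%), close to the stated range. But section 5.1 states 1600 and no such outcome rates. It also picks the hospital as representative of others, and section 7 plans recommendations for hospitals across Rwanda. Inference is meant to go beyond one year's patients at one site, so that correction is not appropriate.
- **Nothing hangs on the margin.** No test or decision threshold uses ±5%. That is true and limits the consequence, but it does not make the stated figure right.

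**Conclusion.** The concern holds in this form. The basis of the precision claim is a quantity the study does not estimate, and no outcome is attached to it. By the usual formula the stated inputs lead to 70 to 73 patients, with about ±6 points at the minimum of 50. At assumed outcome rates of 10% to 50%, with no finite-population correction, the half-width runs from about ±7 to ±14 points. The excess is modest at 10% with 70 patients and marked from 20% upwards. A margin on a proportion cannot describe the precision of mean length of stay or cost at all.

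The conclusion rests on reading ±5% as percentage points, on two-sided intervals, and on inference beyond one year's patients. It does not follow that 50 to 70 patients is an unacceptable size. The protocol sets no precision requirement for any named outcome against which the number could be judged too small.

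**What to change.** In section 5.1, delete the caseload-share basis and the general ±5% statement, keep 50 to 70 patients, and put in their place:

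*The study will enrol 50 to 70 patients. For a proportion estimated in all enrolled patients, the 95% confidence interval half-width is roughly ±6 to 7 percentage points with 50 patients and ±5 to 6 with 70 at a true rate of 5%, ±11 to 12 and ±9 to 10 at 20%, and about ±14 and ±12 at 50%, with no finite-population correction because conclusions are meant to apply beyond one year's patients. For mean length of stay the half-width is about 0.28 SD and 0.24 SD.*

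The ranges run from the normal approximation to the expected exact interval, so the choice of interval method can stay with the SAP. If acceptance is counted among patients offered the programme, its denominator differs and these figures do not apply to it directly.

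The cost is wording only. Enrolment, outcomes and analysis are unchanged; the stated precision becomes less favourable.

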## **5.2. ERAS pathways**

Enhanced recovery after surgery is multimodal and multidisciplinary patient centered care; the patient becomes a true actor of his care. The surgeon, the anesthesiologist and the nurses constitute the trinomial leader. Other specialists are also concerned: physiotherapist, nutritionist, gastroenterologist, etc. (2). This partnership explains the importance of education and enhanced preoperative information during hospitalization (2). The success of this true teamwork requires the concerted writing of protocols, interdisciplinary communication, continuous evaluation of one's practice, and the existence of leadership (31). The team spirit is strengthened (2) (10) (32).

**5.2.1. Principal measures (elements) contained in the ERP, irrespective of the specialty (32)**

Pre-operative Pre-admission	Intra-operative	Post operative	Post Discharge

1. Patient information and education: Patient optimization (Counseling, smoking, alcohol, pain management plan, pre-habilitation of select patients (e.g., diabetic, hypertensive))
 
2. No bowel preparation
 
3. No premedication
 
4. Initial multimodal medications
 
5. Limited fasting (light meal up to 6 hours preoperative)
 
5. Carbohydrate loading (up to 2 hours preoperative) and Glucose control
 
6. Discharge planning, education and home medication plan
	
1. Limited fluid intake (Normovolemia)
 
2. Normoglycemia
 
3. Corticosteroids
 
4. Prevention of hypothermia (Normothermia)
 
4. Antibiotic prophylaxis
 
6. Prevention of PONV
 
7. Minimal invasive access
 
8. Multimodal analgesia and Limitation of opioid use,
 
8. No drain or nasogastric tube
	
1. Multimodal analgesia
 
2. Katamine , IV lidocaine
 
3. NSAIDs for 48 h
 
4. Nausea and vomiting management
 
5. Early mobilization
 
6. No or judicious IV fluid management
 
7. Early re-feeding
 
8. No or rapid removal of the bladder catheter
 
9. Patient/family education (Delirium prevention)
	
1. Risk management (Monitor for symptoms or changes in health to seek assistance)
 
2. Telephone calls and SMS (Follow-up with surgeon)
 
3. Continue therapy and other activities for recovery as planned

*Source: How to implement an enhanced recovery program? Proposals from the Francophone Group for enhanced recovery after surgery (GRACE):*

### **5.2.2. Preoperative evaluation**

All the patients include in the ERAS protocol will undergo a preoperative multidisciplinary evaluation performed by the ERAS team. During this evaluation, all information regarding all the step of the ERAS protocol will be given to the patients and all the information regarding the preoperative step to follow, such as smoking quit or alcohol use. Moreover, information about the entire postoperative ERAS step that the patients needed to follow during the hospitalization will be given. Education and discharge plan will be discussed.

### **5.2.3. Preoperative fasting**

All patients will be allowed to take a regular diet until 6 h and Carbohydrate loading or clear fluids until 2 h before surgery. Thromboembolism prophylaxis with low molecular weight heparins will be administered according to patient's comorbidities.

### **5.2.3. Anaesthesiologic protocol**

No premedication will be administered. Two different types of anesthesiology technique will be used: general anesthesia with local infiltration of the surgical incision. In all cases restricted intraoperative fluid administration (6–8 ml/kg/h) and prevention of hypothermia during surgery will be used. Moreover, no opioids will be used during all the perioperative period. Antibiotic prophylaxis will be given in agreement with the hospital protocol. Analgesia and Prevention of PONV will be given. Immediate postoperative monitoring will be performed in the recovery room where the pain numeric rating scale (NRS) will be routinely evaluated by the anesthesiologist or the NPA.

### **5.2.4. Surgical technique**

Laparoscopic approach with a 4-trocar technique will be the first choice when not contraindicated. No Abdominal drainage, no nasogastric tube, when necessary it will be placed immediately after anesthesia and removed upon awakening. A bladder catheter will be placed if indication and be removed immediately after surgery.

### **5.2.5. Postoperative care**

- Analgesia: IV Paracetamol or Katamine administration when necessary.
- No opioids
- Treatment of Nausea and vomiting when necessary

- Pain assessment every 4 hours using pain NRS scale by nursing staff
- If pain not severe: Paracetamol + Ibuprofen or Diclofenac
- Re-feeding
  - Two to 4H after surgery: Liquid diet and mobilization.
  - Withdrawal of intravenous infusions (0.7–1 ml/ kg/h) was obtained during
  - From 8H: light semiliquid meal
  - From the 12H after surgery: a free diet and patient mobilization was further encouraged and increased gradually. All the meals had to be consumed sitting at the table.
- From 24h after surgery: Blood works (FBC and CRP) and Discharge

#### **5.2.6. Discharge & Post discharge**

The important criteria for the patient's discharge from the hospital are: Normal vital signs and blood works, absence of complications or symptoms, a digestive function enabling the patient to eat without nausea or vomiting, return of intestinal transit with emission of gas (stool not required), autonomy to move and post-operative pain relief with oral analgesics (2).

After the discharge for all the patients, the surgeon will make follow up on phone on day 3, 5 day and day 7 to detect any signs of complications during the first week. If no complaints the out patient clinic evaluation will be planned at 15 and 30 days from the operation. The patient will be given oral analgesia for at least 48 hours.

#### **5.3. Data collection and analysis**

A baseline survey will be conducted to assess the awareness and knowledge of health care professional in charge of perioperative care. From November 2021, we will put in place an ERAS protocol for laparoscopic cholecystectomies. Patients living in Kigali and near Kigali having an easy communication means will be sensitized to adhere to the program.

A multidisciplinary team (Surgeons, Anesthesiologists, nurses, anesthetists and psychologists) will be mobilized to participate in the team. A google sheet questionnaire will be designed to collect information about the awareness and knowledge of perioperative health care professional about ERAS programme and then

a modified ERAS protocol will be put in place and data collection will be done using a coded checklist form and consecutive selection of patients will be done during the study period until we reach at least 50 patients. The operative procedures and instrumentation will be standardized for laparoscopic cholecystectomy, and surgeons who will perform the procedures will be having expertise in laparoscopic cholecystectomy. Reasons for conversion from laparoscopic to open cholecystectomy will be recorded and documented. Emergency patients and patients defined as ASA IV and pediatric patients aged below 16 years will be excluded.

Data will be collected for age, gender, indications for surgery, American Society of Anesthesiology (ASA) class, operative time, adverse events (pain, nausea and vomiting), length of hospitalization, and intra- and post-operative complications. The expenses of surgery and in-hospital care will be calculated and analyzed. On discharge, on day 3 of discharge, day 10, day 15 and day 30 of discharge patient will report outcomes and will be recorded by Surgical Recovery Scale. After discharge, the patients will be called or texted on phone to know about their status and collect information. Data will be recorded using EXCEL. Statistical analysis will be done using SPSS software and the one-way analysis of variance (ANOVA) test, the Chi-square test, and the t Student's test will be used when appropriate for comparisons.

A Univariate analysis will be done to determine variables associated with the length of hospital stay. Pearson's chi square will be calculated to compare variables and..

Continuous variables were presented as mean  $\pm$  standard deviation or median (range) when appropriate and categorical variables will be presented as frequency (percentage). A Univariate analysis will be performed through a stepwise linear regression model using length of hospital stay as dependent variable and age, BMI, gender, ASA score, intraoperative infusions, pain, analgesia, nausea, vomiting, 30 days-readmission rates, presence of complications and mortality as independent factors. Variables with significant link will be crossed with outcome variables to draw their correlation overnight, using Multivariate logistic regression A p value  $< 0.05$  will be considered statistically significant.

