### 8.3. Informed consent

All participants will sign an informed consent during the preoperative evaluation regarding the type of operation and the ERAS protocol application

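### ERAS starting in November 2021 and ending in December 2021 cannot be expected to supply the minimum of 50 patients: the stated caseload gives about 12 to 13, and about 38 to 40 even from July

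*Protocol*

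**What the plan says.** **Start of ERAS.** Section 5.3 first describes a baseline survey of health professionals, then states: "From November 2021, we will put in place an ERAS protocol for laparoscopic cholecystectomies".

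**Sample.** The same section says "consecutive selection of patients will be done during the study period until we reach at least 50 patients". Section 5.1 gives a range and attaches a margin of ±5% to it: "A range of 50 to 70 patients will allow to have a confidence level of 95% that the real value is within" that margin.

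**End.** Section 5.1 says "The study will be conducted in Rwanda at the University Teaching Hospital of Kigali from January to December 2021". The timeframe table in section 9 marks data collection from July to December 2021 and data encoding in January 2022. The budget in section 10 pays for six months of data collection. Section 11 funds data collection and telephone follow-up in the two 2021 quarters and shows zero for both 2022 quarters.

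**Caseload.** Section 5.1 gives "75 cases of laparoscopic cholecystectomies" a year at the hospital and also states: "The population proportion of laparoscopic cholecystectomy is 5% within a total general surgical population size of 1600 patients per year".

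**Who can be counted.** Section 8.3 says "All participants will sign an informed consent during the preoperative evaluation regarding the type of operation and the ERAS protocol application". The proposal is dated June 2021, section 8.4 has ethics review still to come, and section 9 marks that step in June 2021.

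**The concern.** The plan fixes a minimum number, a start, an end and a yearly volume, and the four do not fit together. If the dates are followed, the ERAS sample is a fraction of the stated minimum. If the number is followed, the timetable and the funding run out first.

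The conclusions on safety, length of stay and readmission rest on this sample. Section 2 puts the current complication rate at around 5%. With 12 patients and a true rate of 5%, the chance of seeing no complication is 0.95^12 = 54%, so a clean result would say little about safety. The regression in section 5.3, with 12 candidate factors, depends on the same patients.

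**Working it through.** **Inputs.** Caseload: 75 a year (stated) or 0.05 × 1600 = 80 a year (implied), both section 5.1. Minimum: 50 (section 5.3). Range: 50 to 70 (section 5.1). Monthly rate: 75/12 = 6.25, or 80/12 = 6.67.

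**The plan's own sample figure.** With p = 0.05 and d = 0.05, n0 = 1.96² × 0.05 × 0.95 / 0.05² = 73. With a finite-population correction for 1600, 73/(1 + 72/1600) is about 70, the upper end of the stated range. The lower end does not follow: 50 patients give about ±6.0 points (5.9 with the correction). The calendar problem below does not depend on this.

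**Expected cases by start date, all ending December 2021, before exclusions and refusals.**
- November (2 months): 6.25 × 2 = 12.5; 6.67 × 2 = 13.3. This is 25 to 27% of 50.
- July (6 months): 6.25 × 6 = 37.5; 6.67 × 6 = 40. This is 75 to 80% of 50.
- January (12 months): 75 to 80. This would be enough, but January to June precedes or overlaps the proposal and ethics step, so those months cannot supply patients who consented to ERAS before surgery.

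**Chance of 50 or more** (assumption: Poisson counts at the stated volume, everyone eligible and consenting).
- November: 95% range about 6 to 21; chance below 1 in 10^13.
- July: 95% range about 26 to 53; chance 0.029 at 75 a year and 0.070 at 80 a year.

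**Volume needed for 50.** In two months: 50/2 × 12 = 300 a year, 3.75 to 4 times the stated volume. In six months: 50/6 × 12 = 100 a year, 1.25 to 1.33 times.

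**Time needed at the stated volume.** For 50: 50/6.67 = 7.5 to 50/6.25 = 8.0 months. For 70: 10.5 to 11.2 months.

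**If only 80% are eligible and consent** (an assumption; the protocol gives no shares): 10 to 11 from November, 30 to 32 from July, and 9.4 to 10 months to reach 50.

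**Precision with zero events, exact 95% interval.** 0/12: 0 to 26%. 0/38: 0 to 9.3%. 0/50: 0 to 7.1%.

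**Regression.** Twelve factors, one coefficient each, plus an intercept make 13 parameters. With 12 or 13 patients there are no residual degrees of freedom. With 38 to 40 there are about three patients per factor.

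**Follow-up.** Section 5.2.6 plans a visit 30 days from operation, and section 5.3 a report 30 days from discharge. For patients operated on in December these fall at the very end of December or later, mostly after funded collection has ended.

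**The case against.** **The three dates may not be rival starts.** A reader might infer that January, July and November compete as starting points. The documents do not require that. Section 5.3 puts the staff survey first and ERAS second, so July could open the survey phase and November the ERAS phase. Only January clearly conflicts with the June 2021 proposal. This narrows the point without removing it: under the two-phase reading only November and December remain for ERAS patients, which is the worst case.

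**Enrolment may be open-ended.** The rule to continue until 50 could mean that the calendar gives way, and a longer timetable does not by itself bias results. But the same sentence ties enrolment to the study period, and sections 5.1, 9 and 11 end collection in December 2021. If enrolment is open-ended, those sections are wrong.

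**July is less certain than November.** The volume is a rounded past figure, it arose under the bed shortage described in section 2, and 50 from July needs a rise of only a quarter to a third. The 3 to 7% therefore carries more precision than the inputs allow. That stands: 50 from July is unlikely, not impossible. The November result is not affected.

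**Residence is not a listed exclusion.** Section 5.3 says "Patients living in Kigali and near Kigali having an easy communication means will be sensitized to adhere to the program". A reader might count this as an eligibility limit, but the wording describes a recruitment focus. The listed exclusions are emergencies, ASA IV and age below 16. The counts above make no deduction for residence.

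**No safety threshold is stated.** The protocol sets no target precision for complications, and the 5% describes current practice. The 0/12 interval only illustrates how little so few patients can show.

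**Conclusion.** The conflict is real, and nothing in the protocol resolves it. With ERAS from November and collection ending in December 2021, about 12 to 13 patients are expected against a minimum of 50. With the most favourable start still open after the June 2021 ethics step, July, about 38 to 40 are expected. These figures rest on the protocol's own volume of 75 to 80 a year and are optimistic, because no exclusions or refusals are deducted. The probabilities also assume Poisson counts. It must be corrected, since the stated sample is not what the stated dates and volume deliver. It does not follow that the study is infeasible: 50 patients is within reach if the calendar and the money are extended.

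**What to change.** State one start and one end for ERAS enrolment, separate from the staff survey. Bring sections 5.1, 5.3, 9 and 11 into agreement, and make the sample figure match. There are two ways.

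**Keep December 2021 (the cheaper way).** Replace 50 to 70 by the expected ERAS sample: about 12 to 13 from November, or about 38 to 40 if the true start is July, less exclusions. Withdraw the ±5% statement and report exact confidence intervals for the outcomes. Allow day-30 contacts through January 2022. Replace the 12-factor stepwise and multivariate logistic models by descriptive analysis at 12 to 13 patients, or cut them to very few factors at 38 to 40. The cost is about one more month of follow-up contact, a smaller stated sample, wider intervals and the loss of most or all of the multivariable analysis. A reader might take this for a wording change only; the regression plan shows that it is not.

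**Keep the minimum of 50.** Delete the December end and state that enrolment continues until 50 is reached: about 7.5 to 8 months at the stated volume, longer after exclusions. Schedule encoding and analysis after the last day-30 contact. This delays the report and needs new money. At the section 10 rates, one month costs (3,000,000 + 900,000 + 600,000)/6 = 750,000 FRw.
- If the final follow-up month needs only the 100,000 FRw communication line: 1.5 × 750,000 + 100,000 = 1,225,000 to 2 × 750,000 + 100,000 = 1,600,000 FRw.
- If that month is charged in full: 2.5 × 750,000 = 1,875,000 to 3 × 750,000 = 2,250,000 FRw.

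The range is therefore roughly 1.2 to 2.25 million FRw, or 17 to 32% of the 7,130,000 FRw total. It assumes that the six funded months run from first enrolment; the cost is higher if July to October funds are spent before a November start.
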